Effective Date: 01Nov2021

PROTOCOL LPS17726

Analysis Plan Template

Page 9 of 65

TE	Treatment Emergent
TEAE	Treatment Emergent Adverse Event
V	Visit
W	Week
WHO	World Health Organization
WHODrug	World Health Organization Drug

Document: \\ieedc-

 $vnasc 01 \\BIOS data \\Sanofi \\Fabrazyme \\IAB16602 \\Biostatistics \\Documentation \\SAP \\Sanofi \\Finally \\Sanofi \\Finally \\Finally$

Version\lps17726-16-1-9-sap.docx

Author: Version Number: Final V1.0

Version Date: 22Oct2024

Template No.: CS_TP_BS016 Revision 7 Reference: CS_WI_BS005

Effective Date: 01Nov2021

Page 10 of 65

1 Introduction

This statistical analysis plan (SAP) describes the rules and conventions to be used in the presentation and analysis of safety and tolerability data for Protocol LPS17726. It describes the data to be summarized and analyzed, including specifics of the statistical analyses to be performed.

This SAP is based on protocol version 2.0 (Protocol Amendment Number 1.0), dated 20May2024. Changes to statistical considerations previously defined within the protocol are detailed in Section 3.3 'Changes to Analysis from Protocol'.

2 STUDY OBJECTIVES AND ESTIMANDS

Table A - Objectives and Estimands

Objectives	Estimand Description/Endpoints
Primary	
To investigate the safety and tolerability of the protocol to increase the rate of Fabrazyme infusion with reduced total time and volume of infusion	Population : Participants with confirmed diagnosis of FD, age 2 to 65 years, Fabrazyme-experienced, treated for at least 3 months without IARs during the most recent 3 infusions.
	Treatment : Fabrazyme 1 mg/kg Q2W up to the rate tolerated (refer to Protocol Section 6.2), with oral premedications given 30 minutes prior to each infusion.
	Endpoint : % reduction of infusion duration from prestudy average of recent 3 infusions.
	Intercurrent events: A while-on-treatment approach will be applied, where the % reduction of infusion duration will be derived from the infusions actually received. Participants never observed to tolerate any infusion rate will be counted as having zero percent

Document: \\ieedc-

 $vnasc01\BIOS data\Sanofi\Fabrazyme\IAB16602\Biostatistics\Documentation\SAP\SAP\Sanofi\Final$

Version\lps17726-16-1-9-sap.docx

Author: Version Number: Final V1.0

Version Date: 22Oct2024

Template No.: CS_TP_BS016 Revision 7 Reference: CS_WI_BS005

Effective Date: 01Nov2021

Sanofi-Aventis Recherche & Développement PROTOCOL LPS17726

Analysis Plan Template

Page 11 of 65

reduction. A treatment policy approach will be applied in case pre-medications are not given as described within the protocol. No action will be taken for this event for the analysis even when pre-medications are not given as described within the protocol. Summary measure: Median and quantiles of % reduction of infusion duration from prestudy average of recent 3 infusions.
Population: Participants with confirmed diagnosis of FD, age 2 to 65 years, Fabrazyme-experienced, treated for at least 3 months without IARs during the most recent 3 infusions. Treatment: Fabrazyme 1 mg/kg Q2W up to the rate tolerated (refer to Protocol Section 6.2), with oral premedications given 30 minutes prior to each infusion.
Endpoint: Shortest infusion duration each participant tolerates. Intercurrent events: A while-on-treatment approach
will be applied, the shortest infusion duration will be derived from the infusions actually received. Participants never observed to tolerate any infusion rate will be counted as having duration greater than the maximum observed in their treatment group. A treatment policy approach will be applied in case pre-medications are not given as described within the protocol. No action will be taken for this event for the analysis even when pre-medications are not given as described within the protocol.
Summary measure: Median and quantiles of the shortest infusion duration each participant tolerates.

Document: \\ieedc-

Author:

 $vnasc 01 \\BIOS data \\Sanofi \\Fabrazyme \\IAB16602 \\Biostatistics \\Documentation \\SAP \\Sanofi \\Finally \\Sanofi \\Finally \\Finally$

Version\lps17726-16-1-9-sap.docx

Template No.: CS_TP_BS016 Revision 7

Version Number: Final V1.0

Version Date: 22Oct2024

Reference: CS_WI_BS005

Effective Date: 01Nov2021

Sanofi-Aventis Recherche & Développement PROTOCOL LPS17726

Analysis Plan Template

Page 12 of 65

Secondary		
To investigate the proportion of participants achieving the shortest planned duration of infusion time (20 minutes for participants ≥30 kg and 30 minutes for participants <30 kg) without experiencing any or the second IAR	Population: Participants with confirmed diagnosis of FD, age 2 to 65 years, Fabrazyme-experienced, treated for at least 3 months without IARs during the most recent 3 infusions. Treatment: Fabrazyme 1 mg/kg Q2W up to the rate tolerated (refer to Protocol Section 6.2), with oral premedications given 30 minutes prior to each infusion. Endpoint: Binary: Participant achieved the shortest planned duration of infusion time (20 minutes for participants ≥30 kg and 30 minutes for participants <30 kg) without experiencing any IAR. Intercurrent events: A while-on-treatment approach will be applied. Participants never observed to tolerate any infusion rate will be counted as not achieving the shortest planned duration. A treatment policy approach will be applied in case pre-medications are not given as described within the protocol. No action will be taken for this event for the analysis even when pre-medications are not given as described within the protocol. Summary measure: Number and % of participants achieving the endpoint. Population: Participants with confirmed diagnosis of FD, age 2 to 65 years, Fabrazyme-experienced, treated for at least 3 months without IARs during the	
	FD, age 2 to 65 years, Fabrazyme-experienced,	

Document: \\ieedc-

 $vnasc 01 \\BIOS data \\Sanofi \\Fabrazyme \\IAB16602 \\Biostatistics \\Documentation \\SAP \\Sanofi \\Finally \\Sanofi \\Finally \\Finally$

Version\lps17726-16-1-9-sap.docx

Author: Version Number: Final V1.0

Version Date: 22Oct2024

Template No.: CS_TP_BS016 Revision 7 Reference: CS_WI_BS005

Effective Date: 01Nov2021

PROTOCOL LPS17726

Analysis Plan Template

Page 13 of 65

Endpoint: Binary: Participant achieved the shortest planned duration of infusion time (20 minutes for participants ≥30 kg and 30 minutes for participants <30 kg) without experiencing a second IAR.

Intercurrent events: A while-on-treatment approach

infusion.

Intercurrent events: A while-on-treatment approach will be applied. Participants never observed to tolerate any infusion rate will be counted as not achieving the shortest planned duration. A treatment policy approach will be applied in case pre-medications are not given as described within the protocol. No action will be taken for this event for the analysis even when pre-medications are not given as described within the protocol.

Summary measure: Number and % of participants achieving the endpoint.

 To investigate the proportion of participants achieving infusion duration shorter than
 90 minutes without experiencing any or the second IAR **Population**: Participants with confirmed diagnosis of FD, age 2 to 65 years, Fabrazyme-experienced, treated for at least 3 months without IARs during the most recent 3 infusions.

Treatment: Fabrazyme 1 mg/kg Q2W up to the rate tolerated (refer to Protocol Section 6.2), with oral premedications given 30 minutes prior to each infusion.

Endpoint: Binary: Participant achieved infusion duration shorter than 90 minutes without experiencing any IAR.

Intercurrent events: A while-on-treatment approach will be applied. Participants never observed to tolerate any infusion rate will be counted as not achieving the required duration. A treatment policy approach will be applied in case pre-medications are

Final V1.0

22Oct2024

Document: \\ieedc-

Author:

vnasc01\BIOSdata\Sanofi\Fabrazyme\IAB16602\Biostatistics\Documentation\SAP\SAP\Sanofi\Final

Version Number:

Version\lps17726-16-1-9-sap.docx

Version Date:

Template No.: CS_TP_BS016 Revision 7 Reference: CS_WI_BS005

Effective Date: 01Nov2021

PROTOCOL LPS17726

Analysis Plan Template	Page 14 of
	not given as described within the protocol. No action will be taken for this event for the analysis even when pre-medications are not given as described within the protocol. Summary measure: Number and % of participants achieving the endpoint.
	Population: Participants with confirmed diagnosis of FD, age 2 to 65 years, Fabrazyme-experienced, treated for at least 3 months without IARs during the most recent 3 infusions.
	Treatment : Fabrazyme 1 mg/kg Q2W up to the rate tolerated (refer to Protocol Section 6.2), with oral premedications given 30 minutes prior to each infusion.
	Endpoint : Binary: Participant achieved infusion duration shorter than 90 minutes. without experiencing a second IAR.
	Intercurrent events: A while-on-treatment approach will be applied. Participants never observed to tolerate any infusion rate will be counted as not achieving the required duration. A treatment policy approach will be applied in case pre-medications are not given as described within the protocol. No action will be taken for this event for the analysis even when pre-medications are not given as described within the protocol.
	Summary measure : Number and % of participants achieving the endpoint.

Document: \\ieedc-

 $vnasc 01 \\BIOS data \\Sanofi \\Fabrazyme \\IAB16602 \\Biostatistics \\Documentation \\SAP \\Sanofi \\Finally \\Sanofi \\Finally \\Finally$

Version\lps17726-16-1-9-sap.docx

Author: Version Number: Final V1.0

Version Date: 22Oct2024

Template No.: CS_TP_BS016 Revision 7 Reference: CS_WI_BS005

Effective Date: 01Nov2021

PROTOCOL LPS17726

Analysis Plan Template

Page 15 of 65

Final V1.0

•	To investigate the number and proportion of				
	participants achieving each infusion duration				
	planned in the study without experiencing any or				
	the second IAR				

Population: Participants with confirmed diagnosis of FD, age 2 to 65 years, Fabrazyme-experienced, treated for at least 3 months without IARs during the most recent 3 infusions.

Treatment: Fabrazyme 1 mg/kg Q2W up to the rate tolerated (refer to Protocol Section 6.2), with oral premedications given 30 minutes prior to each infusion.

Endpoint: Binary, calculated separately for each infusion duration: Participant achieved infusion duration without experiencing any IAR.

Intercurrent events: A while-on-treatment approach will be applied. Participants never observed to tolerate any infusion rate will be counted as not achieving the required duration for the infusion. A treatment policy approach will be applied in case pre-medications are not given as described within the protocol. No action will be taken for this event for the analysis even when pre-medications are not given as described within the protocol.

Summary measure: For each infusion duration, number and % of participants achieving the endpoint.

Population: Participants with confirmed diagnosis of FD, age 2 to 65 years, Fabrazyme-experienced, treated for at least 3 months without IARs during the most recent 3 infusions.

Treatment: Fabrazyme 1 mg/kg Q2W up to the rate tolerated (refer to Protocol Section 6.2), with oral premedications given 30 minutes prior to each infusion.

Endpoint: Binary, calculated separately for each infusion duration: Participant achieved infusion

Document: \\ieedc-

Author:

vnasc01\BIOSdata\Sanofi\Fabrazyme\IAB16602\Biostatistics\Documentation\SAP\SAP\Sanofi\Final

Version\lps17726-16-1-9-sap.docx

Template No.: CS_TP_BS016 Revision 7

Effective Date: 01Nov2021

Version Date: 22Oct2024

Reference: CS_WI_BS005

Version Number:

PROTOCOL LPS17726

Analysis Plan Template

Page 16 of 65

	duration without experiencing a second IAR. Intercurrent events: A while-on-treatment approach will be applied. Participants never observed to tolerate any infusion rate will be counted as not achieving the required duration for the infusion. A treatment policy approach will be applied in case pre-medications are not given as described within the protocol. No action will be taken for this event for the analysis even when pre-medications are not given as described within the protocol. Summary measure: For each infusion duration,	
To investigate the influence of increased infusion rate on the immunogenicity and efficacy of Fabrazyme treatment	 number and % of participants achieving the endpoint. Changes of plasma lyso-GL3 from baseline to 6 months follow-up Change of the titer of ADA to Fabrazyme over 	
Safety	6 months follow-up	
To investigate the influence of increased infusion rate on the safety of Fabrazyme treatment	Number, severity, and nature of AEs including IARs	

Abbreviations: ADA = anti-drug antibody, AE = adverse event; FD = Fabry disease; IAR = infusion associated reaction; lyso-GL3 = globotriaosylsphingosine; Q2W = every 2 weeks.

Document: \\ieedc-

 $vnasc01\\BIOS data\\Sanofi\\Fabrazyme\\IAB16602\\Biostatistics\\Documentation\\SAP\\Sanofi\\Finally and the property of the property$

Version\lps17726-16-1-9-sap.docx

Author: Version Number: Final V1.0

Version Date: 22Oct2024

Template No.: CS_TP_BS016 Revision 7 Reference: CS_WI_BS005

Effective Date: 01Nov2021

PROTOCOL LPS17726

Analysis Plan Template

Page 17 of 65

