4.5 End of Treatment Definition	The below paragraphs were edited (deleted text in strikethrough, additions in bold): The end of treatment is defined when the participant successfully reaches the shortest infusion duration planned for the cohort which he/she belongs to or when the participant experiences a second IAR. At that point, the participant will not receive any further infusion as part of the study, regardless of whether the Study Intervention Period reaches 16 weeks or not. The Study Intervention Period will be completed in the absence of IAR at Week 10, or at the latest at Week 16 (Figure 2 and Figure 3).	Correction on end of treatment definition, as in the absence of any IAR during the treatment period, if the current infusion duration for the participant ≥30 kg is 120 minutes (the shortest possible initial duration), then he/she would complete the treatment at Week 8; if the current infusion duration for the participant <30 kg is 90 minutes (the shortest possible initial duration), then he/she would complete the treatment at Week 6.

Section # and Name	Description of Change	Brief Rationale

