7.3.1.1.2 ACTUAL SHORTEST TOLERATED INFUSION DURATION

Participants never observed to tolerate any infusion during the study treatment period will have

Document: \\ieedc-

vnasc01\BIOSdata\Sanofi\Fabrazyme\IAB16602\Biostatistics\Documentation\SAP\SAP\Sanofi\Final

Version\lps17726-16-1-9-sap.docx

Author: Version Number: Final V1.0

Version Date: 22Oct2024

Template No.: CS_TP_BS016 Revision 7 Reference: CS_WI_BS005

Effective Date: 01Nov2021

PROTOCOL LPS17726

Analysis Plan Template

Page 33 of 65

their actual shortest tolerated duration set to their mean (average) pre-study infusion duration. If all pre-study durations are missing and the participant does not tolerate any infusion during the study treatment period, then shortest tolerated infusion duration will be considered missing.

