15 ENDPOINT EVALUATION

15.1 PRIMARY ENDPOINTS

15.1.1 PRIMARY ENDPOINT VARIABLE(S)

15.1.1.1 SHORTEST INFUSION DURATION EACH PARTICIPANT TOLERATES

The shortest infusion duration tolerated is the actual shortest duration (highest infusion rate) of a completed infusion tolerated by the participant without experiencing a second IAR.

A completed infusion is an infusion during which the entire amount of the study drug planned to be given at the visit has been delivered to the participant via infusion and the question "Was the infusion adjusted from the planned infusion?" is answered either "Infusion not changed" or "Infusion interrupted" on the Fabrazyme eCRF page. If the infusion was interrupted, it will only be considered completed if it was restarted, ie, the stop time of study drug infusion is later than the stop time of infusion interrupted.

An infusion is considered tolerated if it is completed within an actual duration (excluding any interruptions) not exceeding 120% of planned duration, without IAR. If the participant receives several infusions at the same planned duration during the study treatment period, the infusion duration will be considered tolerated if the last infusion with the duration is tolerated. Data for infusion duration tolerated at each visit (scheduled and unscheduled) is captured on the Fabrazyme eCRF pages.

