15.1.1.2 PERCENT REDUCTION OF INFUSION DURATION FROM PRE-STUDY AVERAGE OF RECENT 3 INFUSIONS

Percent reduction is with respect to the shortest tolerated infusion for the participant.

The pre-study infusion duration is derived as the average of the duration of 3 most recent

Document: \\ieedc-

 $vnasc01\\BIOS data\\Sanofi\\Fabrazyme\\IAB16602\\Biostatistics\\Documentation\\SAP\\SAP\\Sanofi\\Finally and the properties of t$

Version\lps17726-16-1-9-sap.docx

Author: Version Number: Final V1.0

Version Date: 22Oct2024

Template No.: CS_TP_BS016 Revision 7 Reference: CS_WI_BS005

Effective Date: 01Nov2021

PROTOCOL LPS17726

Analysis Plan Template

Page 44 of 65

infusions the participant received prior to participating to this study. Data for pre-study infusion durations are captured on the Pre-Study Fabrazyme Treatment eCRF page.

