15.1.2 DERIVATIONS

- Infusion Interruption Duration (minutes) = (Interruption Stop Time Interruption Start Time)
- Actual infusion duration (minutes) = (Infusion Stop Time Infusion Start Time) –
 Infusion Interruption Duration (minutes)
- Average of pre-study infusion duration (minutes) = sum of all pre-study infusion duration (minutes) / number of pre-study infusions
- Percentage reduction of infusion duration (%) =100*[(Average of pre-study infusion duration (minutes) Actual shortest infusion duration tolerated (minutes)] /Average of pre-study infusion duration (minutes)
- Percentage change of infusion duration (%) =100*[Actual shortest infusion duration tolerated (minutes) Average of pre-study infusion duration (minutes)] /Average of pre-study infusion duration (minutes)

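### Never-tolerators score 0% on the primary % reduction and can outrank participants who did tolerate an infusion; the SAP imputation carries this into both primary endpoints

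*SAP*

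**What the plan says.** The rules sit in five places.

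- **First primary estimand, % reduction** (SAP Section 2, Table A; same rule in Protocol 1.1 and Protocol Table 2): "Participants never observed to tolerate any infusion rate will be counted as having zero percent" reduction.
- **Second primary estimand, shortest tolerated duration** (same tables): "Participants never observed to tolerate any infusion rate will be counted as having duration greater than the maximum observed in their treatment group".
- **Imputation** (SAP 7.3.1.1.2): never-tolerators have "their actual shortest tolerated duration set to their mean (average) pre-study infusion duration". This one rule feeds both endpoints.
- **Derivation** (SAP 15.1.1.2 and 15.1.2): "Percent reduction is with respect to the shortest tolerated infusion for the participant". The value is 100 times the pre-study mean minus the actual shortest tolerated duration, divided by the pre-study mean. No lower bound is stated.
- **Tolerated** (SAP 15.1.1.1): "An infusion is considered tolerated if it is completed within an actual duration (excluding any interruptions) not exceeding 120% of planned duration, without IAR". Nothing requires a tolerated infusion to be shorter than the pre-study mean.

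Both primary endpoints are summarised by median and quantiles. SAP Section 7 adds mean, minimum and maximum, and SAP 15.1.4 adds waterfall plots of shortest tolerated duration and % change.

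**The concern.** A score assigned to complete failure should not be better than a score that can be observed in someone who partly succeeded. Zero works as a failure score only if no tolerator can fall below it, and the formula does not ensure that. The second primary estimand shows that the plan meant never-tolerators to come last, yet SAP 7.3.1.1.2 gives them a mid-scale duration instead.

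At stake is the lower end of both primary summaries: minimum, mean, possibly the lower quartile, and the order of bars in the waterfall plots. With at most 14 participants, and with confidence intervals dropped (SAP 3.3), each person's position is visible. A choice about how to place failures is better made before the results are known.

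**Working it through.** **Inputs.** The formula is from SAP 15.1.2, the 120% limit from SAP 15.1.1.1, the imputation from SAP 7.3.1.1.2, and n = 14 from SAP 3.1. Target durations of 20 and 30 minutes are from Protocol 4.1, and the labelled minimum of 90 minutes from Protocol 2.1. The starting planned durations are in Figures 2 and 3 and are not shown in the text reviewed.

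**Step 1. Reproduce the plan's 0%.** With the pre-study mean entered as the tolerated duration, 100 × (pre - pre)/pre = 0% at any pre-study mean. Table A and SAP 7.3.1.1.2 agree on this endpoint.

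**Step 2. When does a tolerator score below 0%?** Let p be the planned duration of the shortest tolerated infusion. At the limit the actual duration is 1.2p, and 100 × (pre - 1.2p)/pre is negative when p exceeds pre/1.2, that is, 83.3% of the pre-study mean.

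| Pre-study mean (min) | Planned | Actual | % reduction |
|---|---|---|---|
| any | none tolerated | – | 0 |
| 120 | 120 | 144 | 100 × (120 - 144)/120 = -20.0 |
| 90 | 90 | 108 | 100 × (90 - 108)/90 = -20.0 |
| 120 | 100 | 120 | 0.0 |
| 120 | 90 | 108 | 100 × (120 - 108)/120 = +10.0 |
| 90 | 120 (assumed start) | 120 | 100 × (90 - 120)/90 = -33.3 |
| 90 | 120 (assumed start) | 144 | 100 × (90 - 144)/90 = -60.0 |

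So a step planned at the pre-study duration can give 0% to -20%, while a step at 75% of it cannot go below +10%. The last two rows need a start above the pre-study mean, which is an assumption.

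**Step 3. The second primary endpoint.** Take a never-tolerator with a pre-study mean of 120 minutes and a tolerator whose only tolerated infusion took 144. SAP 7.3.1.1.2 enters the never-tolerator at 120, ahead of the tolerator. Table A would place the never-tolerator above 144. The imputation therefore contradicts Table A and reproduces the inversion on the duration scale.

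**Step 4. Effect at n = 14.** Assume tolerators are either at -20% or at +83.3% (120 to 20 minutes: 100 × (120 - 20)/120). The lower quartile is the 4th ordered value and the median the mean of the 7th and 8th.

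| Never / at -20% / at +83.3% | Rule | Q1 | Median | Mean |
|---|---|---|---|---|
| 1 / 1 / 12 | as written | 83.3 | 83.3 | 979.6/14 = 70.0 |
| | worst rank | 83.3 | 83.3 | tolerators: 979.6/13 = 75.4 |
| 2 / 2 / 10 | as written | 0 | 83.3 | 793/14 = 56.6 |
| | worst rank | -20 | 83.3 | tolerators: 793/12 = 66.1 |
| 4 / 4 / 6 | as written | -20 | 0 | 419.8/14 = 30.0 |
| | worst rank | none tolerated | -20 | tolerators: 419.8/10 = 42.0 |

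Because Q1 is the 4th value and the median starts at the 7th, Q1 can change only with at least 4 participants in the two affected groups combined, and the median only with at least 7.

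**The case against.** Four arguments weigh against the point.

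1. **Zero is a natural value.** Eligibility requires three recent infusions without a reaction, so someone who tolerates nothing in the study has gained no reduction, and 0% says so. This is reasonable as a description. It does not answer the ordering problem, the documents do not give it as the reason, and it is at odds with the worst-rank rule beside it.
2. **The case is rare.** The endpoint uses the shortest tolerated infusion, and durations step down after each success, so a negative value needs someone who tolerates only the earliest steps. An infusion recorded with a rate decrease is not a completed one under SAP 15.1.1.1, which narrows the overrun route. The amendment rationale also reports good tolerance in the first 4 participants. All of this stands and limits the size.
3. **The study is descriptive.** There are no tests, per-participant listings are planned, and SAP 7.3.1.2 counts never-tolerators as non-responders on every secondary endpoint. This also stands.
4. **Large negatives are speculative.** A reader might infer that values such as -33.3% or -60% are built into the design. The only support is an amendment-log rationale, "if the current infusion duration for the participant ≥30 kg is 120 minutes (the shortest possible initial duration". That sentence is tied to the participant's current duration, and SAP 15.2.1.2 provides for planned starts below 90 minutes. The documents do not establish a start above the pre-study mean.

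A reader might also infer that the two primary endpoints order the same people differently. That holds for the Table A text alone. Under SAP 7.3.1.1.2 both endpoints share the inversion.

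**Conclusion.** The scoring defect is real and follows from the SAP's own formula and imputation. Any participant whose shortest tolerated infusion exceeds the pre-study mean ranks below one who tolerated none on % reduction, and SAP 7.3.1.1.2 extends this to shortest tolerated duration, against Table A. Protocol and SAP agree on the 0%, so that value is not a discrepancy between them. The contradiction is between SAP 7.3.1.1.2 and the second primary estimand.

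The size is modest. By overrun alone the negative values are bounded at -20% when the step is planned at the pre-study duration, and they need a step planned above 83.3% of the pre-study mean. The minimum, mean, lower quartile and waterfall order could be affected. The median is safe unless at least half of 14 participants are in the affected groups. It would go too far to say that the reported quartiles will be wrong: the frequency depends on starting durations not shown, and the group sizes in the working are illustrations. It is still worth settling before database lock.

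**What to change.** Before database lock:

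- In SAP 7.3.1.1.2, replace the pre-study-mean substitution with the worst-rank rule already in Table A for shortest tolerated duration.
- Apply the same rule to % reduction in SAP Table A and Protocol Table 2 (and the Protocol 1.1 synopsis that repeats it): never-tolerators rank below the lowest observed value.
- Show them as 'none tolerated' in the quantiles and both waterfall plots.
- Report mean and minimum for tolerators only, always beside the number of never-tolerators.

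The cost is a few sentences and a small programming change. The drawback is that mean and minimum no longer cover everyone when a never-tolerator exists. The tolerator-only mean also looks better (66.1% against 56.6% in the 2 / 2 / 10 illustration), so the count must stand next to it.

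Setting negative values to 0% instead is not recommended. It overwrites observed durations, although the estimand calls for the infusions actually received, and in the 2 / 2 / 10 illustration it leaves Q1 at 0%, the same as now.
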